**Health and Justice: A Continuum of Care for HIV and SU for
Justice-Involved Young Adults (PHASE 2)**

NCT03369249

Study Protocol and Statistical Analysis Plan

(10/20/17)

**Health and Justice: A Continuum of Care for HIV and SU for Justice-involved Youth
(R01 DA 043122)**

**Principal Investigator:
[name]., Columbia University and New York State Psychiatric Institute**

Project Overview

Statement of Responsibility for developing and executing DSMP

The Principal Investigator accepts full responsibility for the development and execution of this Data and Safety Monitoring Plan.

Brief protocol description and study design

This protocol concerns the adaptation, efficacy-testing and implementation evaluation of a multi-component service delivery model (Link2CARE) that aims to increase HIV/STI testing and substance use (SU) screening; reduce HIV and SU risk; and increase linkage to HIV, STI and SU services in justice involved youth (JIY) who are enrolled in an alternative sentencing program (Brooklyn Justice Initiatives; BJI). We propose to adapt and integrate the following evidence-based strategies to create Link2CARE: (i) **Screening**: Offer an onsite rapid oral HIV test and STI urine test at intake into BJI and screen HIV risk behavior and SU; (ii) **Brief intervention**: use brief interventions (1-2 sessions) to reduce HIV risk and SU behavior and promote treatment/service readiness (*MOVE*¹ and *NYSBIRT*^{2,3}); (iii) **Linkage to HIV and SU care**: use a strengths-based patient navigator approach to mobilize JIY strengths and reduce barriers to treatment, while establishing formal relationships and referral protocols with service providers. We have initiated a partnership with BJI, which serves 9000 JIY annually, and Project STAY, a youth-focused, hospital- and community-based, health and HIV treatment program; Project STAY HIV testing outreach workers will be embedded into BJI to deliver Link2CARE. We will test the efficacy of Link2CARE in a randomized controlled trial among N=450 BJI-enrolled JIY (18-24 y.o.), randomized to either Link2CARE or standard of care (SOC) and conduct implementation evaluation to explore individual-, staff, and system-level influences on implementation of this new model to inform scale-up and dissemination. Youth will be assessed at baseline and 3-, 6-, and 12-months post-intervention. BJI and Project STAY staff will be assessed before launch of Link2CARE and 12 and 24 months later.

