DATA MANAGEMENT AND ANALYSIS

Data acquisition, entry and transmission

Study data will be collected in Phases 1 and 2. All Phase 1 and all baseline assessments (Phase 2) will be collected at BJI. Subsequent Phase 2 assessments will occur at BJI, in the participant’s home or at another agreed upon location. Note: BJI is not involved in survey administration, data entry and management, or data storage.

Phase 1: Advisory Panel data: Peer (n=14) and Staff (n=6) Advisory Panels will meet in a series of Panel workgroups during Phase 1 to provide feedback on the adaption of the SU and HIV interventions. Data from these Panel workgroups will be gathered in note form by work group facilitators and will not contain any participant identifying information. These data will be transcribed by research assistants and will be used between workgroups to inform adaptation of interventions.

Pilot data: n=8 youth who participate in a pilot of the SU and HIV protocols will complete paper-and-pencil process measures following the completion of the pilot which will be administered by human subject-trained research assistants (RAs). These research assistants will bring completed questionnaires to the research offices at NYSPI on the day of data collection. These data will be entered in an electronic database by human subject-trained research assistants. This database will be stored on password-protected computers in encrypted files. Researchers will retain the pilot process assessments until the completion of all project activities in Year Five when they will be destroyed following HIPAA standard document destruction services.

Phase 2: Substance use and HIV behavioral risk screen. Following randomization and baseline assessments, n=225 JIY randomized to Link2CARE will complete substance use and HIV behavioral risk screeners. Screening will take place at BJI in private rooms or other agreed upon location (for follow-up survey assessments). Data will be captured on encrypted, password protected computers, entered directly by human subjects-trained RA's into CiW using Sawtooth Software. Sawtooth Software allows for all standard question types, skip patterns, and data piping. Web-based data collection will **not** be used. Following interview completion, RAs will then transport interview data to NYSPI in the encrypted password protected computer, and immediately upload it upon return into the master database at NYSPI held on a secure server.

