HIV and STI testing: Following randomization and baseline assessment, all youth will be offered an HIV and an STI test for Chlamydia and gonorrhea; initial testing will take place onsite at BJI. All youth will also be offered HIV and STI testing at each follow-up interview (3m, 6m and 12m). **HIV testing** will be done using Oraquick advance rapid HIV test. Following brief pre-test counseling, an oral swab will be used to collect saliva to conduct HIV rapid test. Once conducted, the embedded Project STAY staff member (LINK2CARE condition) or human subjects-trained RA (standard of care) will provide results to the participant and HIV+ JIY will be immediately linked to care following Link2CARE linkage protocols. The Project STAY staff or RA will then place the swab in a closed Developer Solution vial, then back into the package. The entire package will be placed in a baggie. The baggie with the used test will be brought back to NYSPI by human-subjects trained RAs and turned in to the Project Director who will enter the results into a the project database at NYSPI that is held on a secure server. The baggie containing the used OraQuick test and materials will then be disposed of in the appropriate waste container. Staff (interviewers and office staff) will wear gloves when manipulating test materials. **STI testing** will occur by the collection and processing of the urine specimens using a Gen-probe APTIMA Urine Specimen Collection Kit for Male and Female Urine Specimens. The testing kits are provided and the urinalysis will be performed by the New York City Department of Health (NYCDOH) at no cost as part of an ongoing agreement with Project STAY. The client is instructed about how to provide the urine sample, and is sent to the bathroom by either the embedded Project STAY staff member (LINK2CARE condition) or human subjects-trained RA (standard of care). Upon return, the Project STAY staff member or RA packages the sample and arranges for pickup by the Department of Health's (DOH) Bureau of STD control. NYCDOH uses the third generation nucleic acid amplification test (NAAT), yielding qualitative testing results. Specimens will be collected and transferred into their respective specimen transport tubes. The transport solutions in these tubes release the rRNA targets and protect them from degradation during storage. When the APTIMA Combo 2 Assay is performed in the laboratory, the target rRNA molecules are isolated from specimens by the use of capture oligomers in a method called target capture. After the target capture steps are completed, the specimens are ready for amplification. The GEN-PROBE APTIMA Combo 2 Assay replicates a specific region of the 23S rRNA from CT and a specific region of the 16S rRNA from GC via DNA intermediates. A unique set of primers is used for each target molecule. Differences in the kinetic profiles of the CT and GC labeled probes allow for the differentiation of signal; kinetic profiles are derived from measurements of photon output during the detection read time. The chemiluminescent detection reaction for CT signal has very rapid kinetics and has the "flasher" kinetic type, while the detection reaction for GC signal is relatively slower and has the "glower" kinetic type. Assay results are determined by a cut-off based on the total RLU and the kinetic curve type. Written documentation of the test results will be obtained by the research office from the NYCDOH Microbiology laboratory within 7 days after the urine sample was delivered. The Project Director who will enter the results into a the project database at NYSPI that is held on a secure server Respondents randomized to Link2CARE who test positive will be informed by embedded Project STAY staff of their results and will immediately be linked to care by STAY staff following Link2CARE linkage protocols. Respondents randomized to SOC who test positive will be contacted by study staff using a succession of methods (telephone, registered letter, and, if refused or undelivered, regular mail). Participants will be informed that antibiotics are used to treat Chlamydia and Gonorrhea. We will counsel that all sex partners within the last 60 days should be evaluated and treated and to avoid sex until they and their partners have been treated for at least 7 days or 7 days after a single dose treatment. Specific referral procedures will be followed to maximize chances that participants will seek treatment.

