Above we described how data are protected during collection and transportation. Once at NYSPI, all data will be saved on secure, password-protected servers. The information gathered will be used only for scientific, educational, or instructional purposes. All interviewers and all other study staff are trained on the importance of subject confidentiality.

REGULATORY ISSUES

Procedures for research team management of AEs, SAEs and other study risks such as mandatory reporting requirements (e.g., child abuse, infectious disease, etc.)

The Principal Investigator, [name] has the ultimate responsibility for reviewing conduct of the study and data produced from it, including the reporting of any adverse events to the respective IRBs.

AEs and SAE that come to the attention of any staff person involved in the study, have to be reported directly to the PI using an *Adverse Event Report Form*. If no action has yet been taken, the PI ensures that these events are addressed by the timely intervention of either herself, [name] or one of the Project STAY staff at BJI. The PI furthermore ensures that the respective IRBs are informed, in line with the seriousness of the event. And follows NYSPI IRB protocol to report (S)AEs and receives feedback about appropriate course of action to follow. Below is a table of potential AEs and SAEs and the proposed procedures to detect them.

Procedures to prevent the violation of confidentiality in accordance with reporting requirements are limited by the mandatory nature of these requirements. Therefore, all subjects are informed in the consent document that the only times other people will find out what they said during the study are: (1) If they describe the physically or sexually abusing a child. This will be reported to the New York State Central Registry (NSCR) which takes calls for child abuse and neglect allegations. If accepted, the NSCR will forward to Bronx field office for the City's Administration for Children's Services (ACS). (2) If they say they want to harm themselves or another person, the researchers can break confidentiality to refer them for further evaluation. (3) In cases of a positive HIV or STI diagnosis, we will follow standard procedures, in line with legal requirements. The mandate for HIV is for the provider doing posttest counseling is to assess for partner notification within 30 days of diagnosis. This will be handled by Project STAY staff or staff from the specific clinic the youth has been

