linked to if not project STAY. Patients will be asked if they can contact sexual partners themselves. If not, sexual partners can be brought in by the patient and clinic staff notifies partners. The third option is to inform the New York City Department of Health and Mental Hygiene (DOHMH), which does anonymous notification and advises sexual partners to go to their physician and get tested. The assessment for partner notification includes a check for domestic abuse risk. For other STIs, partner notification is voluntary not mandatory but Project STAY staff will assess for partner notification and ask the patient to notify partners themselves, the patient can bring partner in, DOHMH can assign a field worker for anonymous notification; Project STAY staff will never call the partner down. All STI, including Chlamydia, Gonorrhea and HIV require an individual, identified report to the city as they occur; this is a direct online report into the DOHMH website.

Table 3 Potential AEs and SAEs and the proposed procedures to detect them.

Types/Categories of Events Anticipated (whether or not occurred)	Procedure to detect
Extreme psychological distress in participants	
 • General follow-up and check-in with all participants during and following each scheduled baseline, 3, 6- and 12-month interviews (Phase 2). • Check-in and debriefing with participants following each HIV/STI testing occasion; pre- and post-interview question “scale 1-10, how do you feel...” • Check-in with provider at 3, 6- and 12-month interviews (Phase 2).
Negative feedback from participant upon debriefing (e.g., thought participation might be harmful or upsetting to others)	
Suicidality (thoughts or intentions)	
Homicidality	
Suspicion of safety concerns in the home	
Increase in sexual risk behaviors or substance use	
Increase in conflict/distress between participants and partners	
Youth detention/incarceration	
Non-voluntary Disclosure of HIV or STI diagnosis	
Non-adherence to treatment and care for HIV+ or STI+ youth	
Loss of Confidentiality	

Staff training (including NIH-required human subjects training and other related training)

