The aims of early interim analyses (in six-month intervals) are to (a) ensure that assumptions about mission-critical parameters (means, standard deviations, and prevalence of main outcomes) made for purposes of power are approximately correct; and (b) to monitor safety of the trial participants, reviewing all adverse events (AEs) and serious adverse events (SAEs). Interim analyses for safety and data monitoring of mission critical parameters, including recruitment and retention rates, will be conducted every 6 months by the trial statistician who will prepare the report for the PSMB (see Monitoring activities below). A third aim of interim analysis is (c) to check at a strategic point in the trial whether sufficiently strong evidence of positive or negative efficacy has accumulated to warrant consideration of stopping the trial (see Trial Stopping above). For all analyses the PI will remain blinded as to treatment assignments. As far as is feasible, the PSMB will also remain blinded, reviewing interim analyses prepared by the unblinded statistician in A/B format. They may, of course, request additional information for any safety concerns or risk-benefit analyses on an as-needed basis. Agreement on these procedures will be obtained with the PSMB prior to trial start. As described above, interim analyses for trial stopping will be conducted once after one-quarter of the 12-month data has been collected.

Monitoring activities

Although the Principal Investigator will have ultimate responsibility for reviewing conduct for the study and data emanating from it, including the reporting of any adverse events to the Institutional Review Boards of Columbia University/the New York State Psychiatric Institute (NYSPI) and NIDA, the PSMB will also review this project twice each year (every 6 months). The Principal Investigator will identify a list of adverse outcomes (e.g., significant psychological distress, loss of privacy) that might occur as a result of participation in the study. In

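### AE capture mixes check-ins common to both arms with staff reports that are likelier in Link2CARE, and the plan does not record which is which, so by-arm AE counts may be inflated in Link2CARE

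*Combined protocol and SAP*

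**What the plan says.** Reporting to the PI is triggered by staff knowledge at any time: "AEs and SAE that come to the attention of any staff person involved in the study, have to be reported directly to the PI" (Procedures for research team management of AEs, SAEs and other study risks). The same section points to Table 3 for the detection procedures, which are three:

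- At the interviews common to both arms: "General follow-up and check-in with all participants during and following each scheduled baseline, 3, 6- and 12-month interviews (Phase 2".
- Whenever a study test is taken: "Check-in and debriefing with participants following each HIV/STI testing occasion", with a pre- and post-interview 1-10 question on how the participant feels.
- Through a provider, who is not defined by arm: "Check-in with provider at 3, 6- and 12-month interviews (Phase 2".

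Study testing is offered in both arms after the baseline assessment, and then: "All youth will also be offered HIV and STI testing at each follow-up interview (3m, 6m and 12m" (Data acquisition, entry and transmission).

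The Link2CARE arm has further contacts. The plan will "use brief interventions (1-2 sessions) to reduce HIV risk and SU behavior and promote treatment/service readiness" and use a patient navigator (Brief protocol description and study design). In addition, "n=225 JIY randomized to Link2CARE will complete substance use and HIV behavioral risk screeners" (Data acquisition, entry and transmission). No matching contacts are described for standard of care (SOC).

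One aim of the six-monthly interim analyses is "to monitor safety of the trial participants, reviewing all adverse events (AEs) and serious adverse events (SAEs" (Plans for Interim Analysis of efficacy data). Under Monitoring activities, the PSMB report contains a description of AEs and SAEs, and the closed session reviews the data by coded arm before advising on continuation. The annual report to NIDA gives the study arm for each AE.

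**The concern.** Staff who meet a participant more often learn of more events. Table 3 lists distress, suicidality, safety concerns at home, conflict with partners and detention. These can come up in a counselling session or a navigator's call and go unmentioned at an interview months later. Link2CARE staff therefore have opportunities to learn of events that have no described counterpart in SOC.

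If the two routes are pooled and shown as A against B, equal true rates could appear as an excess in Link2CARE, and a true reduction could be masked. The PSMB would weigh risk and benefit without a means, in the planned report, of telling extra detection from harm.

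**Working it through.** **What the documents fix.** The plan gives no AE rate, safety sample size or detection probability, so there is no stated figure to reproduce. It does fix the allocation (450 youth, 1:1, so 225 per arm), the common interviews and the Link2CARE-only contacts.

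**The routes side by side.**

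| Route | Link2CARE | SOC |
|---|---|---|
| Check-in at baseline, 3, 6 and 12 months | yes | yes |
| Debriefing after study testing | if test accepted | if test accepted |
| Provider check-in at 3, 6 and 12 months | yes; provider undefined | yes; provider undefined |
| Screeners | yes | not described |
| Brief intervention, 1-2 sessions | yes | not described |
| Patient navigation | yes; number of contacts not given | not described |

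**Illustration (all inputs assumed).** Let the true risk π be equal in both arms. Let s be the probability that an event is found through the scheduled check-ins, the same in both arms. Let u be the probability that the extra Link2CARE contacts find an event that the check-ins missed.

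- Recorded risk in SOC: π·s
- Recorded risk in Link2CARE: π·[s + (1−s)·u]
- Ratio: [s + (1−s)·u] / s, which does not depend on π

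| s | u = 0 | u = 0.1 | u = 0.3 | u = 0.5 |
|---|---|---|---|---|
| 1.0 | 1.00 | 1.00 | 1.00 | 1.00 |
| 0.9 | 1.00 | 1.01 | 1.03 | 1.06 |
| 0.7 | 1.00 | 1.04 | 1.13 | 1.21 |
| 0.5 | 1.00 | 1.10 | 1.30 | 1.50 |

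The ratio is 1.00 if the check-ins find everything or the extra contacts add nothing. Otherwise it exceeds 1.

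**Two cases at 225 per arm.** The chance of a nominal two-sided 0.05 difference against Link2CARE is Φ[(d − 1.96·SE0)/SE1]. Here d is the difference in recorded risk, SE0 its pooled standard error and SE1 its unpooled standard error. With no bias the chance is 2.5%.

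- *Middle case: π = 0.10, s = 0.7, u = 0.3.* SOC is 0.10 × 0.7 = 0.070, or 15.75 youth. Link2CARE is 0.10 × (0.7 + 0.3 × 0.3) = 0.079, or 17.78 youth. The ratio is 1.13. With d = 0.009, SE0 = 0.02476 and SE1 = 0.02475, the chance is Φ(−1.60) = 5.5%.
- *Extreme case: π = 0.20, s = 0.5, u = 0.5.* SOC is 0.20 × 0.5 = 0.100, or 22.5 youth. Link2CARE is 0.20 × (0.5 + 0.5 × 0.5) = 0.150, or 33.75 youth. The ratio is 1.50. With d = 0.050, SE0 = 0.03118 and SE1 = 0.03109, the chance is Φ(−0.36) = 36%.

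The plan specifies no such test. The percentages only show how far a by-arm display could mislead.

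**The case against.** The any-staff sentence is a duty to report, not a counting rule, and its section refers to Table 3, which sets active detection with all participants. A reader might infer that AEs are found only when staff happen to notice them, and so that the comparison is certainly biased. The documents do not support that: the scheduled route is common to both arms, and no bias at all is within the range above.

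A reader might also infer that a formal between-arm AE comparison is planned. It is not. The PSMB report calls for a description of events, and the stopping rule covers two efficacy endpoints only (Trial Stopping Rules). The PSMB may also request listings and any further information it needs (Charge of the HIV Center PSMB). This stands, and it limits the consequence. It does not remove the concern, because the board looks at data by coded arm and would have to ask for a source that no form is said to record.

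Higher test acceptance in Link2CARE might seem to add contacts. But study testing is offered to both arms around the baseline assessment and at the follow-up interviews, where a check-in is already due, so this route probably adds little. Likewise, sexual risk, substance use and attendance at treatment are outcomes measured in both arms, so events of those kinds have a common data source. The asymmetry rests mainly on screeners, sessions and navigation. It would be larger if the provider in Table 3 means the embedded Project STAY staff, which the text does not settle.

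Finally, it is tempting to keep events learned at intervention contacts out of the by-arm comparison altogether. That could hide harms caused by the intervention, such as distress in a session or loss of confidentiality.

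**Conclusion.** The concern holds as a possibility, not as a demonstrated bias. AE capture combines a route common to both arms with one likelier to yield reports in Link2CARE, and the plan neither records nor separates the two. The probable direction is toward more recorded AEs in Link2CARE.

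The size cannot be determined from the documents. With no true difference, scheduled detection of 50% to 100% and extra detection of 0% to 50% of missed events, the recorded ratio lies between 1.0 and about 1.5. If scheduled detection is 90%, it is at most 1.06. These figures rest wholly on assumed probabilities and on the extra contacts having no counterpart in SOC. The documents do not support saying that the comparison is biased, or that equal rates would look like harm.

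**What to change.** Keep reporting and acting on every AE as planned. Then:

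1. Add a field to the Adverse Event Report Form for the contact at which the event was first learned (common interview, testing debriefing, provider check-in, screener, brief session, navigation, other).
2. Give the PSMB, by coded arm, the events elicited by the same questions at the baseline, 3-, 6- and 12-month interviews, with the number interviewed as denominator. Count an event elicited there even if other staff reported it earlier; otherwise Link2CARE would be undercounted. This is the like-for-like comparison.
3. Beside it, show all AEs and SAEs by coded arm and source, including those learned at intervention and testing contacts, with a note that contact is unequal. Exclude none of them.
4. State who the provider in Table 3 is in each arm.

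The cost is one form field, a common set of interview questions, one extra table and one clarifying sentence. The main downside is that the like-for-like table covers only interviewed youth and so depends on retention. At the 25% attrition assumed in the power section, the 12-month column would hold about 225 × 0.75 ≈ 169 per arm, and unequal retention could distort it. The full table by source guards against missing events outside the interviews.
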